| | Safety was determined by comparing safety endpoints to the objective performance criteria (OPC) defined by ANNEX R, Section R2, Table R.1 of BS EN ISO 5840:2009 (Cardiovascular implants – Cardiac valve prostheses) and effectiveness was evaluated based on improvement in NYHA Class and hemodynamic parameters compared to baseline. |
| Trial Design | Prospective, non-randomized, multi-center trial. Pre market analysis was performed when the total late-patient years reached 800 and the number of subjects completing the one year (or greater) follow-up reached or exceeded 300. Post-market, all active subjects will be followed until the last enrolled subject completes their 5-year follow up. |
| Trial Population | The trial population consists of subjects enrolled in the TRANSFORM™ Trial. |
| Number of Subjects | There were 934 subjects enrolled at 29 clinical sites. All active subjects will continue follow up until the last enrolled subject completes their 5-year follow up |
| Gender/Age | Males and females, 18 years of age or older |
| | During the enrollment phase of the trial, the following Inclusion, Exclusion and Intra-operative Exclusion Criteria was required: |

CONFIDENTIAL AND PROPRIETARY DATA: This document and the information contained herein may not be reproduced, used, or disclosed without written permission from Edwards Lifesciences LLC

Inclusion Criteria

1. Male or female, age 18 years or older
2. Has aortic stenosis or stenosis-insufficiency of an aortic valve requiring a planned replacement as indicated in the preoperative evaluation
3. Is scheduled to undergo planned aortic valve replacement with or without concomitant coronary bypass surgery
4. Provide written informed consent
5. Geographically stable and agrees to attend follow-up assessments until all subjects have completed 5 years of follow up

Pre-operative Exclusion Criteria

1. Pure aortic insufficiency
2. Requires emergency surgery
3. Previous aortic valve replacement
4. Had prior mitral, tricuspid or pulmonic valve surgery, which included implant of a bioprosthetic valve, mechanical valve, or annuloplasty ring that will remain *in situ*
5. Requires multiple valve replacement/repair
6. Requires a surgical procedure outside of the cardiac area (e.g., vascular endarterectomy, vascular bypass, tumor removal)
7. Aneurysm of the aortic root and/or ascending aorta requiring surgical intervention

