1.2 EDWARDS INTUITY VALVE SYSTEM

The EDWARDS INTUITY Elite valve system consists of the EDWARDS INTUITY Elite valve, model 8300AB and the EDWARDS INTUITY Elite delivery system, model 8300DB. The pericardial stented aortic valve is based on the design and the proven performance of the PERIMOUNT valve family. A balloon expandable stainless steel cloth-covered frame is incorporated into the inflow aspect of the valve. The valve is implanted with the aid of a delivery system, which incorporates a balloon catheter to expand the frame within the left ventricular outflow tract (LVOT). The expandable frame works in conjunction with the sewing ring to position and stabilize the valve at implant. The system reduces the number

of sutures required to secure the valve, while the frame establishes a seal within the LVOT. The system may be used in both traditional and less invasive surgical procedures for heart valve replacement.

Two generations of the EDWARDS INTUITY Valve System were investigated in the TRANSFORM Trial:

- **GEN-I:** Valve Model 8300ACA and Delivery System Model 8300DCA
- **GEN-II:** Valve Model 8300ACD and Delivery System Model 8300DCD

The GEN-I device was used early on in the IDE trial and was replaced by the GEN-II device.

The trial valve system consists of the trial valve, model 8300ACA, (Figure 1-A) and the trial delivery system, model 8300DCA (Figure 1-C) or trial valve, model 8300ACD (Figure 1-B) and the trial delivery system, model 8300DCD, (Figure 1-D). The trial valve is a modified Carpentier-Edwards PERIMOUNT Magna Ease Aortic bioprostheses (model 3300TFX²).

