1.2.1 MODEL 8300ACA/ACD VALVE DIFFERENCES

Three minor modifications were made to achieve the valve model 8300ACD. 1) In order to enhance seating of the valve during implant the cloth on the frame was shifted down closer to the inflow edge of the annulus frame. Since the cloth on the annulus frame was moved down, the resulting tissue annulus diameter (TAD) was reduced by one mm, which is identical to the model 3300TFX. 2) The single crimped cloth-covered expandable stainless steel frame is now double crimped to further reduce the implant profile. 3) The valve holder is cusp-mounted instead of commissural-mounted to increase the visibility for the nadir suture markers. Also, there was a modification in the method of sewing the holder

onto the valve. Additionally, the holder material was changed to Delrin 500 which is the same material used with all Edwards' valve holders and can now be molded as opposed to machined. Finally, the new holder has a key-lock fitting which is size-dependent to match the modified delivery system, Model 8300DCD.

[figure not shown]
There are no changes to the implant procedure, materials, or packaging. The valve is still attached to the native annulus with only three sutures and uses a pressure-based delivery system to expand the annulus frame. The product name remains the same.

The trial delivery system is designed to introduce the trial valve to the surgical site after removal of the diseased native leaflets. A delivery system is available for each size of the trial valve and consists of the following components:

Model 8300DCA Delivery System

- Balloon Introducer
- Insertion Tool
- Distal Handle
- Frame Expansion Balloon Catheter

[figure not shown]
Figure 1-C: Model 8300DCA Delivery System

Model 8300DCD Delivery System

- Insertion Tool/Balloon Introducer
- Integrated Balloon Catheter

Figure 1-D: Model 8300DCD Delivery System

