1.3 MODEL SECTION

Model 8300ACA/DCA and 8300ACD/DCD were included in the trial. Investigational sites utilizing Model 8300ACA/DCA were transitioned to Model 8300ACD/DCD upon completion of the following; IRB approval, device training and scheduling of investigational product exchange. Each site only had access to either model 8300ACA/DCA or 8300ACD/DCD at any given time. No site had concurrent access to both models.

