4.0 FOLLOW UP PLAN

4.1 TRIAL DESIGN

This is a multi-center, prospective, non-randomized, single-arm, clinical trial to assess the safety and effectiveness of the trial valve system in subjects with aortic stenosis or stenosis-insufficiency requiring primary replacement of the native aortic valve. Premarket analysis was performed when the total late-patient years reached 800 and the number of subjects completing the one year (or greater) follow-up reached and/or exceeds 300. Post-market, all active subjects will be followed until the last enrolled subject completes their 5-year follow up.

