6.2.3 PO YEAR 2 THROUGH SUBSEQUENT ANNUAL VISITS

After the POD 390 visit, the subject will return for follow-up site annually -60/+60 days until the trial ends. The following assessments will be performed:

| | |
|--------------------------------------------------------------|--------------------------------------------------------------------------------------------------------------------------------------------------------------------------------------------------------------------|
| Subject status | |
| Date of Follow-Up | |
| NYHA Classification | |
| Echocardiography (TTE) | Peak and mean pressure gradients, EOA, EOA index, performance index, cardiac output, cardiac index, valvular regurgitation (including paravalvular leak) |
| Electrocardiogram | 12-Lead ECG (Cardiac Rhythm) |
| Anticoagulant therapy/Concomitant cardiovascular medications | Anticoagulants/anti-platelets and other Concomitant cardiovascular medications |
| Coagulation profile | May include PTT or PT or INR if subject is on anticoagulant therapy only |
| Laboratory Testing | WBC, RBC, hemoglobin, hematocrit, platelets, plasma-free hemoglobin (a 2 nd lab draw for plasma free hemoglobin is required within 48 hours if the first draw is >40mg/dl) or haptoglobin or serum LDH |
| Vital signs | Blood pressure, heart rate, weight |
| Adverse events/Complications | If applicable |

At each postoperative assessment, the Investigator will determine the subject's availability for future follow-up visits. If any subject is seen at a time in addition to regularly scheduled follow-up visits, the visit will be recorded as an interim visit. The procedures performed at an unscheduled visit will be at the Investigator's discretion. Available data obtained at an unscheduled visit will be transcribed onto an Unscheduled Visit CRF.

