9.1.3 EFFECTIVENESS ANALYSIS

Subjects will be analyzed according to the NYHA classification preoperatively, at POD 31-46, POD 90-135, and annually post implant for 5 years. The distribution (numbers of subjects and percentages) in the various NYHA classes and the change from baseline (improved, same and worse) will be tabulated and stratified by baseline NYHA at each follow-up interval. Echocardiography data will be obtained preoperatively, intraoperatively, at discharge, POD 90-135, POD 180-240 (optional) and annually post implant until the trial ends. Descriptive statistics for the continuous echo variables (e.g. mean, standard deviation, and range) will be categorized by time interval and valve size. Regurgitation data will be summarized by counts and percentages at each severity level.

A comparison of all effectiveness data for the EDWARDS INTUITY valve will be made to current state of the art prosthetic heart valve literature published in peer reviewed journals at the time of PMA submission.

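### As visible in section 9.1.3, the continuous echo table is not split by device generation, although the GEN-I share very probably rises in Years 6 to 8

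*Combined protocol and SAP*

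**What the plan says.** Section 9.1.3 sets the breakdown of the continuous echo variables: "Descriptive statistics for the continuous echo variables (e.g. mean, standard deviation, and range) will be categorized by time interval and valve size". Section 9.1.1 applies it to the valve implant population as a whole, and section 9.1.5 uses available data without imputation.

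Echo does not stop at Year 5. Section 9.1.3 schedules it at "POD 180-240 (optional) and annually post implant until the trial ends", whereas the same section limits the NYHA analysis to 5 years. Section 6.2.3 agrees: "After the POD 390 visit, the subject will return for follow-up site annually -60/+60 days until the trial ends". Section 4.1 defines the end: "Post-market, all active subjects will be followed until the last enrolled subject completes their 5-year follow up".

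Two device generations were implanted. Section 1.2 says "The GEN-I device was used early on in the IDE trial and was replaced by the GEN-II device". Section 1.3 describes a site-by-site changeover ("Investigational sites utilizing Model 8300ACA/DCA were transitioned to Model 8300ACD/DCD upon completion of the following" IRB approval, training and product exchange), with no site holding both models at once. Section 1.2.1 calls the design changes minor, and notes that, because the frame cloth was moved, "the resulting tissue annulus diameter (TAD) was reduced by one mm". Section 1.2 gives one list of five sizes for the trial valve.

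The synopsis gives the size of the cohort: "There were 934 subjects enrolled at 29 clinical sites". The number of GEN-I implants and the changeover dates are not given. Section 9.0, which introduces the post-approval analyses, is partly blacked out.

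**The concern.** A table by time interval is naturally read along its time axis: a higher mean gradient or smaller EOA at Year 8 than at Year 5 suggests that valves are changing. That reading assumes that the columns describe a similar mix of valves. Up to Year 5 they do, apart from attrition, because every enrolled subject can reach those visits. After Year 5 the stopping rule keeps only early enrollees, and these are the subjects most likely to have GEN-I.

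Valve size does not stand in for generation. Both generations fall under the same labelled sizes, while the tissue annulus diameter differs by 1 mm. The only covariate analysis in the visible text, the hazard regression in section 9.2, concerns reoperation, explant and death, and does not name generation.

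What is at stake is how the Year 6 to 8 columns are read. These are the table's only data beyond Year 5.

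**Working it through.** The plan states no figure for device mix, so there is none to reproduce. The check is calendar arithmetic.

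**Inputs from the documents.** Enrolment ran from 26 September 2012 to 25 August 2016 (section 1.1), which is 1,429 days. There were 934 subjects (synopsis). Year 5 is Day 1825, with a window of Day 1765 to 1885 (Table 1).

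**Assumptions.** Implant day equals enrolment day; accrual is uniform; the trial ends at Day 1825 of the last subject; attrition is ignored. The overall GEN-I share s is not given, so 5%, 10% and 20% are shown.

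**Step 1: who can reach Year k.** A subject can if the enrolment day is at most 1,429 + 1,825 − 365k.

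| Year | Latest enrolment day | Approximate date | Fraction f | Of 934 |
|---|---|---|---|---|
| 6 | 1,064 | August 2015 | 1,064/1,429 = 74.5% | 695 |
| 7 | 699 | August 2014 | 699/1,429 = 48.9% | 457 |
| 8 | 334 | August 2013 | 334/1,429 = 23.4% | 218 |

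For Year 9 the limit is negative (−31), so no one reaches it. The counts are upper limits: echo uses the valve implant population, whose size is not given.

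**Step 2: GEN-I share among those subjects.** If the first-enrolled subjects all received GEN-I (strict order), the share is s/f. For s = 10%: 0.10/0.745 = 13.4%, 0.10/0.489 = 20.4% and 0.10/0.234 = 42.8%. Two softer patterns were also tried. In the gradual switch, the probability of GEN-I falls linearly from 1 to 0 over the first 2s of accrual. In the slow switch, it is 2s over the first half of accrual and then 0.

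| Overall s | Year 6 | Year 7 | Year 8 strict | Year 8 gradual | Year 8 slow |
|---|---|---|---|---|---|
| 5% | 6.7% | 10.2% | 21.4% | 21.4% | 10% |
| 10% | 13.4% | 20.4% | 42.8% | 42.8% | 20% |
| 20% | 26.9% | 40.9% | 85.6% | 70.8% | 40% |

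The Year 6 and 7 columns show strict order; the other two patterns give nearly the same.

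**Step 3: sensitivity.**
- Accrual shape, s = 10%, Year 8: with linearly rising accrual the share is 100% (strict), 86% (gradual) or 20% (slow). With linearly falling accrual it is 24%, 24% or 20%.
- Trial end anywhere in the Year 5 window, strict order, s = 10%, Year 8: 36% to 52%.
- A fixed changeover date instead of a fixed s: a switch 0.5 years after first enrolment gives 13%, 17%, 26% and 55% at Years 5 to 8. A switch at 1 year gives 26%, 34%, 52% and 100%. Staggering the switch over 0.5 to 1.5 years gives 26%, 34%, 52% and 91%.
- Attrition cancels within a column only if it depends on time since implant alone. To hold the Year 8 share at its Year 5 level with the 0.5-year switch, GEN-I retention would have to be 0.12 times GEN-II retention: (0.128/0.872)/(0.547/0.453).

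The share rose after Year 5 in every scenario. Its size varied widely.

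**Step 4: effect on a mean.** With no change within any valve, the pooled mean shifts between Year 5 and Year 8 by d × (share at Year 8 − share at Year 5), where d is the GEN-I minus GEN-II difference. For s = 10% and uniform accrual this is between (0.20 − 0.10)d = 0.10d and (0.428 − 0.10)d = 0.33d. The documents give no value for d. If d = 0, the shift is zero.

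**The case against.** The strongest objection is that no consequence is shown. Section 1.2.1 presents the modifications as minor, directed at seating, implant profile and visibility, with the implant procedure unchanged. It does not say that the orifice changed, and no document reports a difference in EOA or gradient by generation. The figures above measure device mix, not bias. All of this stands, and it limits the point to transparency.

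A reader might infer that the trial cannot tell valve deterioration from device mix. The documents do not support that. Section 10.3 has the Core Lab assess serial studies in the same subject. Structural valve deterioration, reoperation and explant are separate safety endpoints with their own analyses (sections 2.1 and 9.1.2.1). The limitation belongs to one descriptive table.

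Two further objections stand in part. The blacked-out words in section 9.0 may point to a plan that already splits by generation. But section 9.1.3 states its own stratifiers, so the redaction does not clearly cure the gap; a cross-reference would settle it. Section 9.1.3 also does not list the intervals to be tabulated, and Table 1 ends at Year 5. If the table stopped there, the point would fall away, but sections 6.2.3 and 9.1.3 carry echo on to the end of the trial.

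Lastly, late columns also select survivors, early sites and early operator experience. A split by generation does not remove this.

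**Conclusion.** The point holds in a limited form. As visibly written, the continuous echo table omits device generation, and the GEN-I share in its Year 6 to 8 columns very probably rises above the Year 1 to 5 level. The direction follows from GEN-I-first use and the stopping rule, unless retention differs strongly by generation. The size cannot be fixed: for an assumed overall share of 10%, the Year 8 share ran from 20% to 100% across the switch patterns and accrual shapes tried. These are illustrations, not bounds.

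A Year 6 to 8 mean in this table alone therefore does not separate change within valves from device mix. Whether that matters depends on an echo difference between generations that nothing in the documents establishes. No error rate, test or success criterion is affected. This is a low-cost, optional improvement.

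**What to change.** In section 9.1.3, keep the pooled table and add:

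1. the continuous echo variables by generation (GEN-I, GEN-II) within each time interval, with N, and within valve size only where numbers allow;
2. for Years 6 to 8, within-subject change from an earlier postoperative echo (for example the 1-year or 5-year visit), by generation;
3. a statement that both are descriptive, because generation is tied to calendar time, site and operator experience.

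N per generation alone would show the mix but would not separate it from change within valves, which is why item 2 is included. If the blacked-out part of section 9.0 already specifies the split, a cross-reference is enough.

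The cost is a few extra tables. No new data collection should be needed, since section 12.1 requires records of each subject's device exposure. The main downside is small late cells. At s = 10% and uniform accrual, before attrition, Year 8 would hold about 93 GEN-I and 125 GEN-II subjects in strict order (on average 19 and 25 per size over five sizes). With the slow switch it would hold about 44 and 175 (9 and 35 per size). Within-subject change is also limited to subjects with both echoes.

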9.1.4 OTHER OUTCOMES ANALYSIS

The change in Short Form 12 version 1 (SF-12v2) Quality of Life questionnaire from screening to 1 year will be summarized by N, mean, and standard deviation.

Blood data will be analyzed to determine if significant subclinical and unreported hemolysis is occurring due to the implant of the trial valve. A trend analysis of two postoperative data points will be conducted to determine if hemolysis is increasing over time. The following parameters will be included in the trend analysis: plasma-free hemoglobin, haptoglobin, serum LDH, hemoglobin and hematocrit.

For all measured blood parameters, individual results will be compared to documented normal ranges. The Investigator will determine for each parameter that is out-of-range whether the value is abnormal not clinically significant or abnormal clinically significant and summary statistics will be provided.

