During the pre-market phase of the TRANSFORM™ Trial, the EDWARDS INTUITY Valve System (EDWARDS INTUITY Aortic Valve, Model 8300ACA/8300ACD and EDWARDS INTUITY Delivery System, Model

8300DCA/8300DCD) was indicated for use in subjects with aortic stenosis or stenosis plus insufficiency of an aortic valve requiring a planned replacement of their native aortic valve. Post market, the trial device is indicated for the replacement of diseased, damaged, or malfunctioning native or prosthetic aortic valves.

Schedule of Visits

- Screening (Day -90 to Day -1)
- Operative procedure (Day 0)
- Discharge (Post-op – Day of Discharge)
- Postoperative day POD 36 (-5/+10 days; by phone)
- POD 105 (-15/+30 days);
- POD 195 (-15/+45 days); only for subjects with paravalvular leak >mild or an implant related new or worsened cardiac conduction disturbance¹ on 3-month electrocardiogram;
- POD 390 (-25/+45 days)
 - PO Year 2 (-60/+60 days)
 - PO Year 3 (-60/+60 days)
 - PO Year 4 (-60/+60 days)
 - PO Year 5 (-60/+60 days)
- Annually thereafter until the last subject completes 5-year follow-up visit
 - At the time of this protocol revision, all patients had completed these visits

Safety Endpoints

The primary safety endpoints consist of:

- All cause mortality
 - Trial valve-related mortality
- Valve thrombosis (trial valve)
- Thromboembolism
- All hemorrhage
 - Major hemorrhage
- All paravalvular leak (trial valve)
 - Major paravalvular leak (trial valve)
- Endocarditis (trial valve)
- Structural valve deterioration (trial valve)
- Non-Structural valve deterioration (trial valve)

¹ Defined as new or worsened first degree atrioventricular (AV) block, second degree AV block (Mobitz I or Mobitz II), third degree AV block, incomplete right bundle branch block, right bundle branch block, intraventricular conduction delay, left bundle branch block, left anterior fascicular block, or left posterior fascicular block, including block requiring permanent pacemaker implant.

- Valve Malposition
- Valve Migration/ embolization
- Valve Instability
- Valve Dislodgment
- Hemolysis
- Reoperation
 - Trial valve-related reoperation
- Explant
 - Trial valve explant
- Implant-related new or worsened cardiac conduction disturbance
 - requiring permanent pacemaker implant
 - not requiring permanent pacemaker implant

The Data Monitoring Committee (DMC) will conduct a final meeting after the last subject has completed their 5-year follow up

**Effectiveness
Endpoints**

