The following effectiveness endpoints will be assessed:

- Device technical success is defined as the successful delivery and deployment of the trial valve with maximum of two attempts and subject leaving the OR with valve in place
- Procedural success is defined as device technical success followed by the absence of adverse events resulting in device reoperation implant of permanent pacemaker (with baseline sinus rhythm and no other pre-existing conduction issues), or valve-related death within discharge or 10 days post index procedure, whichever comes first.
- Cross-clamp time (for labeling claim)
- Cardiopulmonary bypass time (for labeling claim)
- Length of time in the intensive care unit
- NYHA functional class compared to baseline
- Hemodynamic performance (mean gradient, peak gradient, effective orifice area [EOA], EOA index, performance index, cardiac output [CO], cardiac index [CI], valvular regurgitation [including

paravalvular leak] confirmed by echocardiography and Core lab evaluation)

Other Outcomes

The following data also will be collected:

- Change in Quality of Life questionnaire Short Form 12 version 2 (SF-12v2) from Screening to 1 year
- Laboratory testing (White Blood Cell Count, Red Blood Cell Count, Hemoglobin, Hematocrit, Plasma-free Hemoglobin or haptoglobin or serum LDH, Platelet Count) at screening, discharge and at 3, 6, and 12 months and annually thereafter at each follow-up visit

ABBREVIATIONS

| | | | |
|-------|---------------------------------------------------|-------|--------------------------------------------|
| ACC | American College of Cardiology | IRB | Investigational Review Board |
| AE | Adverse Event | ISO | International Standardization Organization |
| AHA | American Heart Association | LVOT | Left Ventricular Outflow Tract |
| AS | Aortic Stenosis | MI | Myocardial Infarction |
| ASD | Atrial Septal Defect | MOF | Multi-system Organ Failure |
| AVR | Aortic Valve Replacement | MR | Magnetic Resonance |
| CABG | Coronary Artery Bypass Graft | NSVD | Nonstructural Valve Dysfunction |
| CEC | Clinical Events Committee | NYHA | New York Heart Association |
| CFR | Code of Federal Regulations | OPC | Objective Performance Criteria |
| CO/CI | Cardiac Output/Cardiac Index | PFO | Patent Foramen Ovale |
| CRF | Case Report Form | PMA | Premarket Approval |
| CV | Critical Value | PO | Postoperative |
| CVA | Cerebrovascular Accident | POD | Postoperative Day |

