2.3 OTHER OUTCOMES

The following outcomes for additional evaluation are:

- Change in Short Form 12 version 1 (SF-12v2) Quality of Life questionnaire from Baseline to 1 year
- Laboratory testing (White Blood Cell Count, Red Blood Cell Count, Hemoglobin, Hematocrit, Plasma-free Hemoglobin or haptoglobin or serum LDH, Platelet Count) at screening and at 3, 6, 12 months and annually thereafter from post implant

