7.0 SAFETY ASSESSMENTS

Safety assessments will include examination and reporting of adverse events, ECGs, laboratory parameters, vital signs and any changes from baseline.

Adverse events, whether observed by the Investigator or reported by the subject, will be recorded on the Adverse Event CRF. At each visit, the Investigator or designee will determine whether any adverse events occurred by evaluating the subject. Adverse events may be observed directly, reported spontaneously, or identified by questioning the subject at each trial visit. Questioning subjects should be in a general way, without asking about the occurrence of any specific symptoms. The Investigator must appraise all trial related laboratory values. The Investigator should follow subjects with adverse events until the event has resolved or the condition has stabilized.

CONFIDENTIAL AND PROPRIETARY DATA: This document and the information contained herein may not be reproduced, used, or disclosed without written permission from Edwards Lifesciences LLC

Pre-existing medical conditions or symptoms reported prior to device implant will not be recorded as an AE. In the event there is worsening of a pre-existing medical condition or symptoms following the index procedure, then an AE must be recorded. The adverse event report should note the existence of pre-index procedure history when appropriate.

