9.0 STATISTICAL METHODS

The following section describes only those activities that will be conducted after the approval of the study product. All detailed analyses conducted for the PMA submission are XXXX and a xxxx all post approval analyses.

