9.1.5 MISSING DATA

All statistical tests on the effectiveness endpoints will be performed using only those subjects with available data required for endpoint analysis. No missing value imputation will be performed.

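### Section 9.1.4 judges whether hemolysis is increasing from two postoperative points although at least six routine draws are scheduled through Year 5; modelling all of them is a cheap, optional improvement

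*Combined protocol and SAP*

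**What the plan says.** Section 9.1.4 (Other Outcomes Analysis) asks whether the valve causes subclinical, unreported hemolysis and whether it grows. Its method for the second question is: "A trend analysis of two postoperative data points will be conducted to determine if hemolysis is increasing over time". It then lists five markers: "The following parameters will be included in the trend analysis: plasma-free hemoglobin, haptoglobin, serum LDH, hemoglobin and hematocrit". It adds normal-range comparisons and summary statistics for all measured blood parameters.

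Two other places bear on this. Section 7.0 says: "Safety assessments will include examination and reporting of adverse events, ECGs, laboratory parameters, vital signs and any changes from baseline". Section 9.0 points to detail that is blacked out: "All detailed analyses conducted for the PMA submission are XXXX and a xxxx all post approval analyses".

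The laboratory schedule is given twice. The synopsis (Other Outcomes) has tests "at screening, discharge and at 3, 6, and 12 months and annually thereafter at each follow-up visit". Section 2.3 has them "at screening and at 3, 6, 12 months and annually thereafter from post implant", with no discharge draw. The 6-month visit (POD 195) is required only after paravalvular leak above mild or an implant-related conduction disturbance (Section 6.2.1). Annual visits run until the trial ends (Section 6.2.3).

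At each draw, plasma-free hemoglobin, haptoglobin and serum LDH are alternatives to one another. Hemoglobin and hematocrit are listed for every draw (Sections 6.2.3 and 7.9).

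**The concern.** The question is about change over time in a valve followed for at least five years. An early shift that then stays flat and a rise that is still going on at Year 5 mean different things for such a device. A contrast of two visits can show that they differ, but not which of these patterns produced the difference. The draws that could tell them apart are already scheduled. No visible passage plans a trend analysis of these markers beyond two points.

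There are two secondary issues. A pair of visits close together would estimate a slope poorly. And because three of the markers are alternatives, a subject may not have the same one at both chosen visits.

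**Working it through.** The plan gives no standard deviation, effect size, alpha or power for this analysis. There is therefore no stated figure to reproduce, and no power claim is made here.

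**1. Draws available.** By Section 2.3, leaving out the conditional POD 195 visit, the routine postoperative draws through Year 5 are at 3 months, 1 year and Years 2, 3, 4 and 5, which makes six. The synopsis adds discharge, which makes seven. Enrollment ran from September 26, 2012 to August 25, 2016 (Section 1.1), about 3.9 years. The first subject is thus about 8.9 years out when the last reaches Year 5, and early enrollees have further annual draws. Six is the lower count.

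**2. Shape (no variance assumption needed).** Times in years are 105/365.25 = 0.287, 390/365.25 = 1.068, then 2, 3, 4, 5. Compare two courses, each rising 1 unit in total:
- Steady rise: 1/(5 − 0.287) = 0.212 per year throughout.
- Step between 0.287 and 1.068 years, then flat: slope 0.000 from 1 year on.

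Both differ by 1.00 between 3 months and Year 5, so that contrast cannot tell them apart. A pair of 3 months and 1 year gives (1.068 − 0.287) × 0.212 = 0.166 against 1.00. That difference still does not reveal the later course.

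**3. Precision, simplest case.** Assume a random intercept, independent residuals and complete data. The slope variance is then proportional to 1/Sxx, where Sxx is the sum of squared deviations of the visit times from their mean. All six draws give Sxx = 15.93. A pair gives (difference in time)²/2. The ratio of standard errors is √(15.93/pair Sxx).

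| Pair | Pair Sxx | SE ratio |
|---|---|---|
| 3 months, Year 5 | 11.10 | 1.20 |
| 1 year, Year 5 | 7.73 | 1.44 |
| 1 year, Year 2 | 0.435 | 6.05 |
| Year 4, Year 5 | 0.500 | 5.64 |
| 3 months, 1 year | 0.304 | 7.23 |

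**4. Precision over a range of assumptions.** With total variance at time 0 set to 1, the following were varied: between-subject share 0.3, 0.5, 0.7; serial correlation of residuals 0, 0.3, 0.5, 0.8 per year; random-slope SD 0, 0.05, 0.1, 0.2 per year; attrition 0, 4, 8% per year. The all-draw variance is the slope element of the inverse of the sum of p·X′V⁻¹X over dropout patterns, where p is the share of subjects in each pattern. The pair variance is c′Vc divided by the share still observed at the later visit. The standard error ratios are:
- 3 months against Year 5: 1.00–1.28 (1.07–1.28 with independent residuals; 1.00–1.11 at serial correlation 0.8).
- 1 year against Year 5: 1.04–1.53.
- 3 months against 1 year: 1.75–7.23.
- Other adjacent visits: 1.67–6.05.

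**5. Marker switching.** Assume a subject has a given marker at each draw with probability q, independently. The share with it at both visits of a fixed pair is q². The share with at least two values among six draws is 1 − (1−q)⁶ − 6q(1−q)⁵. For q = 0.5 these are 25% and 89%; for q = 0.8, 64% and 99.8%. At q = 0.5, 89 − 25 = 64% of subjects thus have two or more values but not the fixed pair. Subjects with a single value add little. If 10 to 50% of subjects had only one, keeping them would lower the slope standard error by 0.3 to 5.4% (random intercept only, within-subject correlation 0.3 to 0.7).

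**The case against.** The strongest reply has four parts.

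- **The visits and method may be stated in blacked-out text.** Section 9.0 refers to such material. This stands: a reader might infer that the pair is left open, or open to choice after the data are seen, but the documents do not support that. What remains open to comment is the stated number of points, two.
- **The large precision losses need a narrow pair.** Nothing visible says that one will be used, and 3 months against Year 5 is at least as natural for this question. This also stands. For that pair the loss is between none and 28%.
- **Marker switching is assumed.** The documents allow alternatives but do not say that subjects change between them. If each keeps one marker, nothing is lost, and hemoglobin and hematocrit are unaffected by design. Section 9.1.4 could also mean two points per subject, such as first and last available, in which case the fixed-pair shares do not apply.
- **A mixed model with linear time also returns one slope and shows no shape.** This is correct, so the model needs visit as a category. Summary statistics tabulated by visit would also show shape, but Section 9.1.4 does not say that they will be by visit.

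None of this removes the limit in step 2, which holds for any chosen pair of visits.

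**Conclusion.** The point holds as a cheap, optional improvement to an exploratory outcome. Two points cannot show whether a change in hemolysis markers came early and stopped or is continuing, and at least six routine draws that could show it are already scheduled. This part rests on no variance assumption.

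The precision gain rests on assumed variance components. It is small or nil against the widest pair (ratio 1.00–1.28) and large only against adjacent visits (about 1.7–7.2). The gain from marker switching rests on an assumed switching pattern.

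A reader might go further and infer that the safety assessment of hemolysis is weak. The documents do not support that. Hemolysis is a safety endpoint in Section 2.1, and Section 9.1.2.1 covers it by early percentages, linearized late rates and Kaplan-Meier. A reader might also look to "No missing value imputation will be performed" in Section 9.1.5 for or against a model, but that section concerns tests on the effectiveness endpoints, so nothing is drawn from it here.

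**What to change.** In Section 9.1.4, replace the two-point trend with a repeated-measures mixed model for each of the five markers:

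- Use all routine scheduled draws from POD 90–135 onward, up to any explant of the trial valve.
- Fit visit as a category to show shape, and report a linear slope as the summary. Use a log scale where suitable.
- Summarize POD 180–240 values separately, because that visit is triggered by findings at 3 months.
- Use the first value when plasma-free hemoglobin is redrawn, because the redraw is triggered by a high result.
- Report the number of subjects contributing per marker.
- Keep the individual normal-range checks, since a mean trend can miss hemolysis in a few subjects. A named two-visit contrast may stay as a summary.
- Add one simple sensitivity analysis for dropout, for example slope by last-visit group.

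Separately, reconcile the synopsis with Section 2.3 on whether a discharge draw is part of the laboratory schedule.

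The cost is SAP wording, modest programming and reliance on missing at random, which the dropout analysis checks. No extra draws or visits are needed. If the planned pair is 3 months against Year 5 and subjects keep one marker, the benefit is mainly the view of shape.
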